## 5) Statistical Design:

The objective of this study is to assess muscle stiffness and microvascular perfusion before and after a 30-minute myofascial massage and to investigate the additional effect of patient-therapist communication. Our primary hypothesis (H1) is that muscle stiffness will be decreased and microvascular perfusion will be increased and that these effects will be enhanced when patient-therapist communication is permitted. We will test this hypothesis with a repeated-measures ANOVA. The outcome variables will be shear wave velocity as representative measure of muscle stiffness and color pixel density indicating microvascular blood flow. Time (before, immediately after, and 60 minutes after massage) will be the within-subjects factor, and communication (permitted or restricted) will be the between-subjects factor. Interaction between time and type of communication will also be assessed. Our secondary hypothesis (H2) is that scores on the Global Satisfaction with Treatment questionnaire will be higher when patient-therapist communication is permitted during the massage treatment compared to communication restricted. We will test this hypothesis with a two-sided independent t-test.

The proposed study is a pilot investigation with shear wave velocity of the pectoralis major as primary outcome. Changes in shear wave velocity after myofascial massage have not been investigated previously. Thus, a formal power analysis was not completed. We estimate that if a moderate-to-large effect size is observed ( $f = 0.25-0.4$ ), our analysis plan can detect a significant within-between interaction (e.g., time by type of communication) with 8-18 participants (assuming alpha = 0.05, power = 80%, 2 groups, 3 repeated measures and correlation = 0.7). Accounting for data loss and study dropouts, we request to recruit 30 participants to complete this work.

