## STUDY SYNOPSIS

Title	Effects of myofascial massage and patient-therapist communication on shoulder muscle properties in breast cancer survivors with myofascial pain
Methodology	Longitudinal
Study Duration	1 year
Study Location	School of Kinesiology Building, University of Michigan
Objectives	To assess how myofascial massage and patient-therapist interaction alter the stiffness and microvascular perfusion of shoulder muscles
Number of Subjects	30 participants
Inclusion Criteria	
 
Female sex
 
Age 18 years or older
 
Previous unilateral breast cancer diagnosis
 
Treatment for primary breast cancer was completed 3 months to 2 years prior to enrollment (defined as completion of all treatments except oral maintenance therapies)
 
Myofascial pain in upper quadrant of the chest
 
Ability to understand and willingness to sign a written informed consent.
 

Exclusion Criteria	
 
Chronic neuromuscular or orthopedic injury currently affecting upper extremity function that is unrelated to their cancer diagnosis
 
Currently undergoing physical therapy, occupational therapy or other treatment for side effects related to their cancer diagnosis or other injury to the upper extremity
 
History of fibromyalgia
 
Broken or bruised skin in the chest/shoulder area
 
Diagnosed with metastatic breast cancer
 
Currently receiving treatment for other forms of cancer
 

Study Product(s)	Participants will be randomized 1:1 to receive one 30-minute myofascial massage either with patient-therapist communication permitted or restricted. Stiffness and microvascular perfusion of shoulder muscles will be measured non-invasively before the intervention, immediately afterward, and 60 minutes afterward. Muscle stiffness will be measured using ultrasound shear wave elastography, and microvascular perfusion will be measured with ultrasound-Doppler techniques. Participants will complete a questionnaire to assess the satisfaction with their treatment.
Statistical Methodology	A repeated-measures analysis of variance will be used to compare muscle stiffness and microvascular perfusion between intervention groups and their interaction. A two-sided independent t-test will be used to test for differences in treatment satisfaction between the groups.

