## 1) Study Objectives:

The objective of the proposed study is to assess how myofascial massage alters stiffness and microvascular perfusion of shoulder muscles and how these changes are influenced by patient-therapist communication. Specifically, we will examine superficial shoulder muscles in breast cancer survivors before and after they receive one session of myofascial massage. Participants will be randomized 1:1 to receive massage where communication with the massage therapist is permitted or restricted. Our primary hypothesis is that stiffness of shoulder muscles will be decreased, and microvascular perfusion will be increased after a 30-minute myofascial massage, and that the addition of patient-therapist communication will result in greater changes than massage alone with patient-therapist communication restricted. Our secondary hypothesis is that treatment satisfaction will be higher when communication is permitted compared to when communication is restricted.

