Participants will be randomized into two groups. One group will receive the massage treatment while the massage therapist will be permitted to more readily communicate with the participant, and one group will receive the same massage treatment while the massage therapist will restrict communication with the participant to only essential exchanges. When communication is permitted, the therapist will have a short consultation with the participant, explaining the massage techniques used and asking for specific areas of shoulder/chest discomfort/pain to focus the treatment on. During the treatment, the therapist and the participant will be allowed to converse freely. The therapist will ask for feedback regarding the massage technique applied and will adjust the technique (duration, intensity) accordingly. When communication is restricted, the massage therapist will only provide essential information about the treatment (how to get ready, when treatment will start and finish) to the participant. The participant will not be instructed to limit conversation (e.g. to alert the therapist if the intensity is too much), but the therapist will limit their responses.

We will withhold information about grouping and randomization from the participants until they complete the study visit to avoid a possible confounding effect of having this knowledge. We do not expect any adverse effects from withholding this information from the participants as all participants will receive the same standardized massage treatment. All participants will be handed a sealed envelope after the study which includes a letter informing them of the restricted/unrestricted communication component of the research study as well as the group for which they had been assigned.

Randomization will be done using covariate adaptive randomization controlling for the covariates of age and body mass index. A study coordinator will randomize participants and print each participant's group membership on a piece of paper, which will be placed in a sealed envelope. The envelope will be given to the massage therapist before meeting with the participant. Only the study coordinator and the massage therapist will have knowledge of each participant's group membership. All other research personnel involved in data collection (including those actively collecting ultrasound images) and analysis will be blinded to group membership until data analysis is complete for all participants.

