## 6) Objectives and Endpoints:

OBJECTIVES	ENDPOINTS	JUSTIFICATION FOR ENDPOINTS
Primary		

OBJECTIVES	ENDPOINTS	JUSTIFICATION FOR ENDPOINTS
1. To quantify changes in muscle stiffness in response to myofascial massage.	Change in muscle stiffness of the pectoralis major will be assessed by ultrasound shear wave elastography before and after myofascial massage	Muscle stiffness is hypothesized to decrease after myofascial massage is completed compared to baseline.
Secondary		
1. To quantify changes in muscle perfusion in response to myofascial massage.	Change in muscle perfusion of the pectoralis major and upper trapezius will be assessed by Doppler imaging and superb microvascular imaging before and after myofascial massage	Perfusion to muscle tissue undergoing massage is hypothesized to increase after myofascial massage is complete compared to baseline.
2. To evaluate the effect of patient-therapist communication on changes in muscle stiffness in response to myofascial massage.	Change in muscle stiffness of the pectoralis major will be assessed by ultrasound shear wave elastography and compared between patients randomized to a group with restricted or unrestricted communication with the massage therapist.	Effects of myofascial massage on muscle stiffness is hypothesized to be enhanced in patients without restricted communication with their massage therapist.
3. To evaluate the effect of patient-therapist communication on satisfaction with treatment	Responses to the Global Satisfaction with Treatment questionnaire will be compared between patients randomized to a group with restricted or unrestricted communication with the massage therapist.	Satisfaction with treatment is hypothesized to be enhanced in patients without restricted communication with their massage therapist.

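### The between-arm stiffness and perfusion comparison omits baseline adjustment and a sphericity correction; adding both is a cheap improvement

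*Combined protocol and SAP*

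**What the plan says.** Section 5 says of the primary hypothesis: "We will test this hypothesis with a repeated-measures ANOVA". The factors are time at three levels, the pre-massage measurement being one of them ("Time (before, immediately after, and 60 minutes after massage) will be the within-subjects factor"), and communication as the between-subjects factor. It adds: "Interaction between time and type of communication will also be assessed". The sample-size sentence says the plan "can detect a significant within-between interaction (e.g., time by type of communication) with 8-18 participants", at f = 0.25-0.4, alpha 0.05, 80% power and correlation 0.7.

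Other places bear on which term answers the communication question:

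- Section 1 predicts that "the addition of patient-therapist communication will result in greater changes than massage alone with patient-therapist communication restricted".
- Section 6 lists as secondary objective 2: "To evaluate the effect of patient-therapist communication on changes in muscle stiffness in response to myofascial massage". Its endpoint is the change in pectoralis major stiffness, compared between arms.
- The synopsis puts the group comparison beside the interaction: "A repeated-measures analysis of variance will be used to compare muscle stiffness and microvascular perfusion between intervention groups and their interaction".

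On covariates, Section 4 says: "Randomization will be done using covariate adaptive randomization controlling for the covariates of age and body mass index". Its confidentiality text mentions height, weight and ethnicity as possible covariates. Nothing in the document adjusts for baseline stiffness or perfusion, and nothing mentions sphericity or a correction for departures from it.

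**The concern.** With baseline as an outcome level, the interaction compares raw changes from baseline between arms. A raw change subtracts the whole baseline value even though baseline predicts the later value only in part (0.7 on the plan's own assumption). Part of any chance baseline difference therefore enters the estimate. Allocation balances age and body mass index, not baseline stiffness or perfusion.

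The three-level F tests also assume sphericity. If the two post-massage values correlate more with each other than with baseline, which is plausible, the uncorrected F test rejects a true null too often.

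Finally, the communication main effect averages in a pre-massage difference that is null by randomization, and no sentence says that this term is not the communication test.

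At stake is the width of the interval for the communication effect, which a pilot needs for planning, and modest control of type I error.

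**Working it through.** **Inputs.** From Section 5: N = 30, two arms, three measurements, correlation rho = 0.7, alpha 0.05, f = 0.25-0.4. From Section 1: 1:1 allocation, so 15 per arm. Assumptions, because the document gives no figures: complete data, unit SD, equal correlations unless stated, and true effects in SD units.

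**1. The plan's own figure.** Noncentral F with lambda = f² × N × 3/(1 − rho) and 2 and 2(N − 2) df.
- f = 0.4, N = 8: power 81%.
- f = 0.25: N = 16 gives 77%, N = 18 gives 82%.

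The stated 8-18 reproduces, with sphericity assumed. At N = 30 and f = 0.25, lambda = 0.0625 × 30 × 3/0.3 = 18.75 and power is 97.3%.

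**2. What f means here.** For an effect d present equally at both post-massage times, f = d/√18. So f = 0.25-0.4 is d = 1.06-1.70 SD, and d = 0.7 SD is f = 0.165, below the plan's range. At 0.7 SD the planned interaction has 70% power.

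**3. Variance with and without baseline adjustment** (per person, SD² units, rho = 0.7).
- One post time: change 2(1 − rho) = 0.60; adjusted 1 − rho² = 0.51; ratio 0.85.
- Mean of both: change (1 + rho)/2 + 1 − 2rho = 0.45; adjusted (1 + rho)/2 − rho² = 0.36; ratio 0.80.

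| rho | ratio, one time | ratio, mean of both |
|---|---|---|
| 0.5 | 0.75 | 0.67 |
| 0.7 | 0.85 | 0.80 |
| 0.9 | 0.95 | 0.93 |

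**4. Interval width and power** (15 per arm; t with 28 df unadjusted, 27 df adjusted; adjusted variance multiplied by 1 + 1/26 for estimating the slope).
- One time: 95% CI half-width 0.58 to 0.55 SD (6% narrower); power at 0.7 SD 67% to 72%.
- Mean of both, effect sustained: 0.50 to 0.46 SD (8-9% narrower); power 79% to 86%.

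**5. Chance imbalance.** The baseline difference between arms has standard error √(4/30) = 0.37 SD. A one-standard-error imbalance moves the unadjusted change difference by 0.37 × (1 − 0.7) = 0.11 SD.

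**6. Sphericity.** Simulated trials of 30 with no effect, at assumed correlations:

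| baseline-post / post-post | mean epsilon | uncorrected type I error |
|---|---|---|
| 0.7 / 0.8 | 0.90 | 5.2% |
| 0.7 / 0.9 | 0.75 | 6.3% |
| 0.6 / 0.9 | 0.69 | 6.7% |

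Greenhouse-Geisser gives 4.7-4.9% in all three. Its cost in nominal power at a sustained 0.6 SD is about 1 point if sphericity holds (56% to 55%) and about 6 points at 0.6/0.9 (51% to 45%). Part of the latter is the excess error rate being removed.

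**7. Main effect.** The difference is 2d/3 with variance factor (1 + 2rho)/3 = 0.80. For a sustained effect, power is 28% at 0.7 SD, 55% at f = 0.25 and 92% at f = 0.4.

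**The case against.** The strongest reply is that the plan already works where it says it will. At f = 0.25 the interaction has 97% power with 30 participants. It is unbiased under randomization, and the 0.11 SD shift is chance variation that the interval already covers. All of this stands, so the point is about precision and robustness.

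A second reply is that the power gains in step 4 start from a single-contrast change-score test, not from the planned 2-df test. This is also right. At 0.7 SD the interaction has 70%, so a baseline-adjusted contrast at one time gains 2 points over it. For the mean of both times, 70% to 79% comes from choosing the contrast and 79% to 86% from the adjustment. Nor should the 2-df test be dismissed. If the effect appears at one time only (0.7 SD), the adjusted mean of both has 33% power against 70% for the interaction, and a contrast at the wrong time has 5%. Section 5 says these changes have not been studied before, so a test that does not depend on the time course is defensible.

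A reader might also infer that the main effect is the planned communication test and would usually miss a real effect. The document does not support this. Sections 1, 5 and 6 speak of enhanced changes and size the study on the interaction. For a sustained effect in the plan's range, even the main effect has 55-92% power.

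The type I figures rest on assumed correlations, since the plan gives only 0.7. What survives is that baseline is measured in everyone before massage and left unused as a covariate, and that a standard correction is not named.

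**Conclusion.** The point holds as a cheap improvement, not as an error in the planned test. At the plan's correlation of 0.7, with 15 per arm and complete data, baseline adjustment lowers the variance of the between-arm contrast by 15-20%. The gain is larger at correlation 0.5 (25-33%) and small at 0.9 (5-7%). Greenhouse-Geisser removes a possible type I excess of 0.2 to 1.7 percentage points under the assumed correlations.

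The consequence is mainly for secondary objective 2 in Section 6, which Sections 1 and 5 also fold into the primary hypothesis. The same reasoning covers perfusion. A reader might conclude that the primary before-after stiffness result is compromised. It is not: with complete data and equal arms, the pooled change from baseline is the same number under the ANOVA and under a common-baseline model. Which term decides the communication question can be inferred from the text; stating it is a clarification.

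**What to change.** In Section 5 and the synopsis:

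1. Report the between-arm differences immediately after massage and at 60 minutes, each with a 95% CI and adjusted for the baseline value of that outcome. ANCOVA at each time would do. So would a mixed model of all three times with a common baseline mean, which also uses participants with a missing measurement.
2. Apply a Greenhouse-Geisser correction to the time and interaction F tests.
3. State that the interaction, not the communication main effect, is the communication test.

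Replacing the 2-df interaction with one named contrast is optional. It gains power only if the effect has the expected shape, and the contrast would have to be fixed before unblinding.

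The cost is a few sentences, slightly more analysis code and about one degree of freedom. Greenhouse-Geisser costs about 1 point of power under sphericity and several points under marked non-sphericity. No extra measurements or participants are needed.

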After baseline measurements are completed, participants will be taken to the massage room where they will meet the massage therapist. Participants will be asked to remove all upper body clothing before lying down face up on the massage bed. They will be asked to cover their bodies, including chest and shoulders, with a sheet and woolen blanket. The massage therapist will leave the room while the participants get ready. Once the participant is ready, the massage therapist will re-enter the room and begin the myofascial massage. The treatment will last 30 minutes and focus on the chest and shoulder of the side that received the cancer treatment. Techniques applied during the intervention will include skin glide (variable time), stroking (2-3 minutes), scar tissue rolling (2-3 minutes), strumming (2-3 minutes), fascial stretch (3-5 minutes), circular friction (1-2 minutes), deep fascial release (3-5 minutes) and arm pull (60 seconds). The timing and order of each element will be varied based on tissue response and patient feedback. The massage therapist will carefully expose areas of the chest and/or shoulder to perform the treatment. A massage oil may be applied to the participant's skin if necessary. After the conclusion of the massage treatment, the massage therapist will leave the room so that the participant can get dressed again. No research personnel will be present in the massage room during the entire time.

Immediately afterward, participants will return to the examination room, where the measurements conducted at baseline will be repeated. Participants will then remain in the clinical suite (or an adjacent waiting room) for 60 minutes, after which all measurements will be repeated a second time. During their 60-minute wait period, participants will be asked to fill in the treatment satisfaction questionnaire. Additionally, participants will be allowed to keep themselves occupied (e.g., reading), and they will be allowed to use the TV entertainment system provided in the examination room.

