This experiment carries a small (\$30) nominal payment that is not contingent upon successful completion of the study. Compensation will be in the form of a gift card. This study provides a small direct benefit to the participants resulting from the massage treatment. Risks associated with the treatment intervention are no more than minimal and include mild soft tissue discomfort during the massage treatment and possible muscle soreness the next day. To avoid/minimize discomfort during the treatment, the massage therapist will adjust the treatment accordingly. For participants that withdraw early, we will prorate this payment at \$15 per hour, rounded to the nearest 20-minute interval, up to a maximum payment of \$30.

All data will be stored by randomized study ID for each participant. All data collected during the appointment will be kept in a secure U-M database. There will be one document linking the ID numbers to the identifiers, which will be kept in a locked cabinet within a card-locked laboratory or key-locked office. Only members of the study team will have access to the document. This will be kept for 12 months after the study is completed, as it may be needed during the analysis of the data. Twelve months after the conclusion of the study, all identifiable information will be destroyed.

\*\*\* Begin **Ame00163783** \*\*\*

All data will be stored by randomized study ID for each participant. All data collected during the appointment will be maintained in REDCap, which is password-protected, with only the study team members able to access identifiable information. There will be one document linking the ID numbers to the identifiers, which will be kept in a locked cabinet within a card-locked laboratory or key-locked office. Only members of the study team will have access to the document. This will be kept for 12 months after the study is completed, as it may be needed during the analysis of the data. Twelve months after the conclusion of the study, all identifiable information will be destroyed.

\*\*\* End **Ame00163783** \*\*\*

All data collected during the research, including self-reported information from breast cancer survivors about their diagnosis and treatment, will be saved only under their randomized study ID. Data will be stored on password-protected devices inside a card-locked laboratory and separate from any documents containing any personally identifiable information.

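### The only analysis named for stiffness and perfusion is a three-time-point repeated-measures ANOVA with no rule for incomplete women, so by default a missing 60-minute set also removes the baseline and immediate values

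*Combined protocol and SAP*

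**What the plan says.** Section 5 (Statistical Design) gives one method for the primary hypothesis: "We will test this hypothesis with a repeated-measures ANOVA". Its factors are three-level time ("Time (before, immediately after, and 60 minutes after massage) will be the within-subjects factor"), group ("communication (permitted or restricted) will be the between-subjects factor") and their interaction. The synopsis names the same method. Neither place gives an analysis population, a missing-data rule, an imputation method or a separate two-point contrast.

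On the primary endpoint, section 5 says "The proposed study is a pilot investigation with shear wave velocity of the pectoralis major as primary outcome", and section 6 (Objectives and Endpoints) says "Change in muscle stiffness of the pectoralis major will be assessed by ultrasound shear wave elastography before and after myofascial massage". Section 6 does not say whether the post-massage value is the immediate one, the 60-minute one or both.

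The visit sequence is in section 4 (Experimental Design). After the massage, "Immediately afterward, participants will return to the examination room, where the measurements conducted at baseline will be repeated". A 60-minute wait follows, and then a third set of measurements. The session lasts about 2 hours.

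Incomplete data are foreseen in two places. The payment terms in section 4 begin "For participants that withdraw early, we will prorate this payment at" and go on to an hourly rate. Section 5 ends its sample-size paragraph with "Accounting for data loss and study dropouts, we request to recruit 30 participants to complete this work". Neither gives an expected rate.

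**The concern.** A classical repeated-measures ANOVA works on complete rows. Because the immediate scan comes before the wait, a woman who leaves during the wait already has a usable before-and-after pair. The same is true of a woman whose whole 60-minute set proves unusable. Unless the plan says otherwise, the named method sets that pair aside.

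Two things are at stake. The first is precision: measurements already collected in a 30-person pilot go unused. The second is bias. If women who respond less are more likely to miss the third set, those who remain are a favourable selection, and the softening after massage is overstated. In addition, how incomplete women are handled would be decided after the data are in hand.

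**Working it through.** **Inputs from section 5.** Alpha 0.05, power 80%, 2 groups, 3 repeated measures, correlation 0.7, f = 0.25 to 0.4, stated need 8 to 18 participants, recruitment 30.

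**Assumed, because the documents give no figure.** The number of women without a usable 60-minute set; a true baseline-to-immediate change of -0.30 SD; the strength of any link between response and leaving.

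**1. The plan's own figure.** For the within-between interaction, with sphericity, the noncentrality is λ = N × 3 × f² / (1 − 0.7), with df1 = (2 − 1)(3 − 1) = 2 and df2 = (N − 2)(3 − 1).
- f = 0.4, N = 8: λ = 8 × 3 × 0.16 / 0.3 = 12.8, df2 = 12, power 0.810.
- f = 0.25, N = 18: λ = 18 × 3 × 0.0625 / 0.3 = 11.25, df2 = 32, power 0.825.

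These are the smallest N that reach 80%, so the stated 8 to 18 reproduces exactly.

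**2. Does the method need complete rows?** A standard repeated-measures ANOVA routine (AnovaRM in statsmodels) was given data with one time point missing for one participant. It refused them as unbalanced.

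**3. Random loss of the 60-minute set.** All 30 women have the baseline and immediate pair, and the ANOVA uses only complete cases. The standard error of the change is inflated by √(30 / complete cases). Interaction power uses the formula in step 1 with f = 0.25.

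| Lost of 30 | Complete cases | SE ratio | Interaction power |
|---|---|---|---|
| 0 | 30 | 1.00 | 0.973 |
| 1 (3%) | 29 | √(30/29) = 1.02 | 0.968 |
| 3 (10%) | 27 | √(30/27) = 1.05 | 0.955 |
| 6 (20%) | 24 | √(30/24) = 1.12 | 0.928 |

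Random loss causes no bias.

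**4. Loss related to response.** With unit SD and correlation 0.7, the SD of the change is √(2 × (1 − 0.7)) = 0.775. Leaving follows a logistic model in the observed baseline-to-immediate change, with the intercept set to give the stated loss. The table gives the complete-case mean change when the truth is -0.30 SD.

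| Odds of leaving per SD of weaker softening | 1 of 30 lost | 10% lost |
|---|---|---|
| 1.5 | -0.31 | -0.33 |
| 2 | -0.32 | -0.35 |
| about 4.5 (log-odds 1.5) | -0.34 | -0.40 |

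An estimate from every woman with both values returns -0.30 throughout.

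**5. Does the alternative work at this size?** In 300 simulated trials of 30 women, with about 20% loss and the strongest selection above, a REML mixed model on all available values gave -0.29 (Monte Carlo SE 0.008). Complete cases gave -0.46.

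**The case against.** The best defence is that little is likely to be lost. Stiffness and perfusion are measured at one visit of about 2 hours, the treatment is described as minimal risk, and women may read or watch television during the wait. Each stiffness set has three images from each of nine pectoralis regions, so one poor image need not remove anyone. Participants cannot see their shear wave velocity, and no document links it to leaving. At 10% loss, even the strongest selection assumed shifts the estimate by about 0.10 SD, less than the standard error of the change (0.775 / √30 = 0.14). All of this stands, and it limits the size of the point.

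The defence can add that recruiting 30 covers dropout. That is true for power, but a larger sample does not remove selection bias.

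Three stronger readings are tempting, and the documents do not support them.
- A reader might infer that such a woman has both of her primary measurements. Section 6 does not say that the immediate value is the primary one. If the 60-minute value counts, she lacks a primary measurement, although her other two values are still left unused.
- A reader might infer that the plan orders deletion. It does not. It is silent, and deletion is the default of the method it names.
- A reader might take the gap between 18 and 30 as an expected 40% loss. Section 5 states no rate, and the same reasoning from 8 would imply 22/30 = 73%. The allowance also covers losses before the immediate scan, for which no analysis can recover a before-to-immediate change.

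Finally, a one-line missing-data rule or a paired baseline-to-immediate contrast would also address the narrow problem. That is fair, but the mixed model does so while keeping the planned time-by-communication structure.

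**Conclusion.** The point holds in a limited form. The single named method drops incomplete women by default, nothing in the plan overrides that, and incomplete data are foreseen. The likely cost is modest: a standard error 2% to 12% larger for random loss of 1 to 6 women, with interaction power of at least 0.928 at f = 0.25. The bias is conditional. It arises only if leaving is related to response, and the range of -0.33 to -0.40 for a true -0.30 at 10% loss rests on assumed odds of 1.5 to about 4.5 per SD. With one woman lost it is about -0.31 to -0.34. Different leaving by arm could in principle also distort the communication contrast, but nothing in the documents allows that to be sized. The change is worth making because it is nearly free and should be settled before data are seen, not because a large error has been shown.

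**What to change.** In section 5:
- State which post-massage time point (immediate, 60-minute or both) defines the primary endpoint, and align section 6 with it.
- Replace the repeated-measures ANOVA with a linear mixed model with time, communication and time-by-communication, fitted by REML with small-sample degrees of freedom. Use all available measurements from every randomised woman with at least one measurement, in her assigned group.
- Take the primary contrast from that model.
- Report the number of women contributing at each time point, by arm.

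This takes a few lines, with no new data, visits or participants. With complete, balanced data and compound symmetry (non-negative between-person variance) the model reproduces the ANOVA, so nothing is lost if nobody leaves. The cost is that a covariance structure must be named in advance and data assumed missing at random given the observed values. If leaving depends on the unseen 60-minute value itself, the model does not fully correct for it.
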